| 
Eligibility criteria
     | 
10
  | 
Participants. The individual hospital sites and their acute care teams will be the focus of the CP implementation. Participants at each site will include acute care physicians and nurses, as well as hospital administrators with responsibility for the acute care settings. For the purposes of evaluating the impact of the CP on health outcomes, participants will be children 5 to 18 years of age diagnosed with concussion, as well as their parents. Children 4 years of age and younger are excluded because measures of post concussive symptoms and other clinical outcomes have not been validated for those ages. We will standardize the identification of concussion to include all patients diagnosed with ICD code S06.0 (concussion). We also will include all patients diagnosed with S09.9 (head injury, unspecified) in a sensitivity analysis, and work with AHS analytics to determine whether to recode such cases to code S06.0 when appropriate.
  |
| 
Interventions
            | 
11a
 | 
Intervention strategy. Our first objective is to develop an intervention strategy that promotes uptake of the CP at each site. Because our choice of intervention strategy depends on input from each site, we cannot fully design the intervention until the study begins. However, we have provisionally chosen three core intervention components based on previous CP implementation efforts: (1) a local champion team at each site; (2) a reminder system (i.e., placement of the 5P sticker, information leaflets, and website flyer onto patient charts); and (3) a patient and parent website that provides important information about concussion recovery (see Table 2 on next page); (4) regular teleconferences with site champions to discuss progress; and (5) teaching sessions for physicians and nurses at each site prior to rollout. These components address health professional, acute care team, and organizational (site) issues. Based on site input, we may refine these strategies or add others. In general, though, the implementation strategy will be designed to work within existing hospital resources, to ensure feasibility and sustainability, minimize reliance on study support and infrastructure, and assess implementation in a realistic context.
 |

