11b *Theory-based design with knowledge user input.* Our intervention strategy will be based on the TDF, which provides an evidence-based, theory-driven approach to informing intervention design. Prior to implementing the CP, a TDF-based structured interview guide will be used to elicit barriers and facilitators to implementation from relevant stakeholders through site visits and key informant interviews. Site visits also will be used to assess organizational issues, such as flow of pediatric patients, health provider roles, and experience with CPs in the acute care setting. During each visit, we will interview physicians and nurses to elicit clinical or procedurally important barriers and facilitators to implementing the CP. In addition, one administrator at each site will be interviewed to determine readiness for change, as well as barriers and facilitators, at the organizational level. Site visit interviews will be audiotaped and transcribed for subsequent analysis. The site visit process will promote understanding of site-specific issues and increase project engagement.

11c *Table 2: Core components of implementation strategy*

| Core component                      | Description   |
|--|--|
| Local site champion teams                  | -Nurse educator or emergency nurse
-Emergency medicine/acute care physician   |
| Pre-implementation site visits             | -Assessment of local ED/acute care attitudes, organization, and feedback on CP usability   |
| Ongoing site support                       | -Monthly teleconferences with site teams
-Weekly emails to all clinical teams for pathway utilization   |
| Reminder systems for health care providers | -CP specific tools for physicians assessing patients (eg. 5P sticker on patient charts)
-Referral to concussion clinic for children at high risk of persistent postconcussive symptoms  |
| Patient and parent engagement              | -Reminders to use CPs in patient care areas
-Family handout given at discharge with concussion care instructions and reminders to access the web portal
-Patient and parent-friendly website to provide tools to track recovery and information about concussion recovery and care |
| Site commitment                            | -Facilitation through site approval processes
-Prioritization within other site initiatives   |

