The third phase of the project will involve data analysis, which is expected to take 6 months. The final phase will involve dissemination of the study findings to all study sites and associated stakeholders, as well as to broader clinical and scientific audiences through conference presentations and journal publications. Within the context of the broader MNCY concussion workgroup, we also will begin planning for the scaling up of CP implementation on a province-wide level. The complete study is expected to take 3 years.

13b

| Project Activity               | Project Year |   |   |   |   |   |
|--------------------------------|--------------|---|---|---|---|---|
|                                | 1            |   | 2 |   | 3 |   |
| Hire & train personnel         | ■            |   |   |   |   |   |
| Pre-implementation             |              |   |   |   |   |   |
| Project site visits            | ■            | ■ |   |   |   |   |
| Key informant interviews       | ■            | ■ |   |   |   |   |
| Intervention mapping & design  |              | ■ |   |   |   |   |
| Site approvals                 |              | ■ |   |   |   |   |
| Launch meeting & site training |              | ■ |   |   |   |   |
| Randomization                  |              | ■ |   |   |   |   |
| Implementation                 |              |   |   |   |   |   |
| Collect data                   |              | ■ | ■ | ■ |   |   |
| Data analysis                  |              |   |   |   | ■ |   |
| Dissemination                  |              |   |   |   |   |   |
| Study site presentations       |              |   |   |   |   | ■ |
| Stakeholder presentations      |              |   |   |   |   | ■ |
| Conference presentations       |              |   |   |   |   | ■ |
| Journal publications           |              |   |   |   |   | ■ |
| Plan implementation            |              |   |   |   |   | ■ |

Sample size

14

*Analysis Strategy.* Characteristics of patients and sites will be summarized by exposure status (i.e., control versus intervention) to allow for consideration of possible selection biases. Relevant comparisons will include the number of pediatric patients with concussion at each site before and after the implementation of the CP, site characteristics such as total patient volume, and important patient characteristics, including age and sex.

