*Power calculation.* Power calculations for the primary outcome, time to symptom resolution, were computed using standard methods for two-group survival analyses (i.e., children who received care before versus after implementation of the CP). We conservatively assumed a sample size of 1,575, based on a total of 2,100 concussions per year across sites, a 50% rate of web site usage, and 18 months of recruitment. If we assume equal numbers of cases in the pre- and post-implementation phases, a median time to symptom resolution of 4 weeks, non-informative censoring because follow up will continue for 3 months, and no clustering effects, then the minimum hazard ratio that we can detect with .80 power at a significance level of .05 would be 1.20, which would represent at 20% higher likelihood of symptom resolution at any given time post-injury after implementation of the CP. Analyses will treat the randomised crossover from control to intervention as having occurred at the planned time, irrespective of any delays in actual implementation of the intervention, although secondary analyses will explore the effects of the actual timing of the crossover should any delays occur. All sites have provided written commitment to the study. Therefore, barring exceptional circumstances, no sites will be lost to follow-up.

Randomization

15

A study statistician will use a computerized algorithm to select a randomly generated order of implementation for the four sites.

Recruitment 16 Recruitment will rely on ongoing support and communication with clinicians. To avoid having implementation become stalled or displaced by other priorities, we will conduct monthly teleconferences with site champions to discuss progress and sustainability. Teleconferences will allow sites to discuss best practices and local solutions to common barriers. Additionally, the study coordinator and PI will be available for more informal consultation by email or phone.

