## Ethics and dissemination

|                          |     |  |
|--------------------------|-----|--|
| Research ethics approval | 23  | Approval will be obtained by the Conjoint Health Research Ethics Board at the University of Calgary.   |
| Protocol amendments      | 24  | Amendments will be submitted to the research ethics board.   |
| Consent or assent        | 25a | Consent will be obtained from sites through signed agreements. Participant consent will be passively collected when families voluntarily access the web portal and provide electronic consent.   |
| Confidentiality          | 26  | Confidentiality will be maintained by assigning all participants who use the web portal with an identification number. All data collected during the study will use that number for identification purposes. Computer databases will use the identification number for designation purposes, and will not contain participant names. Results from the project will be reported in aggregate format. If individual materials are presented, all personal identifiers will be removed. These safeguards should maintain confidentiality and minimize any risks associated with participation in the project.   |
| Declaration of interests | 27  | There are no declarations of interest to disclose on behalf of the investigators.  |
| Access to data           | 28  | The final dataset will only be accessible to the study team and will not include patient identifiers.  |

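### The invitation to the portal, the only source of the primary outcome, is listed as part of the CP, so entry to the analysed sample may differ by phase and bias the hazard ratio either way

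*Protocol*

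**What the plan says.** **Source of the primary outcome.** Time to symptom resolution rests on weekly reports by patients and parents (items 12b and 12c, Table 3). Families enter these on the portal themselves, without the study team (item 20a), and may stop at any time (item 17b). Entry is voluntary: "Participant consent will be passively collected when families voluntarily access the web portal and provide electronic consent" (item 25a). Families may also use the portal anonymously (items 12a and 17a).

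**What brings families to the portal.** Item 11a, on the provisional core components of the intervention, describes the reminder system as "placement of the 5P sticker, information leaflets, and website flyer onto patient charts". Table 2 (item 11c), on the implementation strategy, lists a family handout at discharge with "reminders to access the web portal". Item 12a also describes a discharge handout. Its front page sends families to the portal and its last four pages give concussion education. Item 12a does not say in which phase it is given. It does say that the portal runs before and after the CP, collects the same ratings in both, and gives evidence-based recovery information only afterwards. Item 19a makes the website version and the text messaging depend on phase, but does not say whether the invitation does.

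**Safeguards.** Item 14 has patient and site characteristics "summarized by exposure status (i.e., control versus intervention) to allow for consideration of possible selection biases", and names age and sex as patient characteristics. Item 19a follows the crude survival curves with Cox models adjusted for variables it does not name.

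**Planning assumptions.** The power calculation in item 14 uses "a 50% rate of web site usage, and 18 months of recruitment" and "equal numbers of cases in the pre- and post-implementation phases", that is, one uptake rate for both phases.

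**The concern.** A family enters the primary analysis by its own choice, after its site's phase is already fixed. Randomising the order of four sites balances nothing about that choice. If the prompt to register is stronger after the CP, the post-CP sample can contain a different mix of fast and slow recoverers from the pre-CP sample.

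Suppose the extra promotion mainly brings in mild cases that would not otherwise have registered. Post-CP recovery then looks faster although the CP has done nothing. If it mainly brings in families of children with lasting symptoms, a real benefit is hidden or a harm appears. At the protocol's own 50% usage, half of the diagnosed children are outside the primary analysis, so there is room for such a shift.

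**Working it through.** **The plan's own figures.** "We conservatively assumed a sample size of 1,575" reproduces: 2,100 × 0.50 × 18/12 = 1,575. With "a median time to symptom resolution of 4 weeks" in controls, a hazard ratio of 1.20, equal groups and T = 12 or 13 weeks of follow-up, expected events are 1,575/2 × [(1 − 2^(−T/4)) + (1 − 2^(−1.2T/4))] = 1,412 or 1,439. The smallest detectable hazard ratio at 80% power (two-sided 0.05 assumed) is exp[2(1.960 + 0.842)/√events] = 1.16. The stated 1.20 is therefore conservative for its own inputs. That is separate from this point, and 1.20 is used below only as a yardstick.

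**Bias model, no CP effect.** From the documents: 15–25% of children have persisting problems (item 6a), overall median about 4 weeks, 3 months of follow-up (item 14). Assumed: 20% slow recoverers with median 12 weeks, 80% fast with median 3.2 weeks, exponential times, and all uptake rates by recovery speed. The mixture's overall median solves 0.20 × 2^(−t/12) + 0.80 × 2^(−t/3.2) = 0.5, which gives t = 3.9 weeks.

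Slow share among portal users = 0.20·u_slow / (0.20·u_slow + 0.80·u_fast). Example: pre 0.14/(0.14 + 0.36) = 28.0%; post 0.14/(0.14 + 0.48) = 22.6%.

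The large-sample Cox hazard ratio θ solves ∫[f1 − (f0 + f1)·θS1/(θS1 + S0)] dt = 0 over 13 weeks, where S and f are the mixture survival and density pre (0) and post (1). The rejection rate is approximately Φ(|ln θ|·√1,340/2 − 1.96) plus the small opposite tail, taking about 1,340 events (85% of 1,575).

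| Uptake slow/fast, pre | post | Slow share pre → post | Null HR | Rejection rate |
|---|---|---|---|---|
| 70/45% | 70/60% | 28.0 → 22.6% | 1.07 | 24% |
| 70/45% | 70/70% | 28.0 → 20.0% | 1.11 | 46% |
| 80/40% | 80/65% | 33.3 → 23.5% | 1.13 | 61% |
| 70/45% | 80/60% | 28.0 → 25.0% | 1.04 | 11% |
| 70/45% | 75/50% | 28.0 → 27.3% | 1.01 | 5% |
| 50/50% | 75/50% | 20.0 → 27.3% | 0.91 | 39% |
| 50/50% | 60/60% | 20.0 → 20.0% | 1.00 | 5% |

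The first row starts from the protocol's own 50% overall uptake (0.14 + 0.36) and rises to 62%. Fewer children than 1,575 would lower the rejection rates but not the bias in the hazard ratio.

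**What a spurious 1.20 would take.** With the slow share at 15–25% post-CP, a slow median of 12–16 weeks and an overall median of 4 weeks, a null hazard ratio of 1.10 needs the slow share to fall by about 6–8 points at crossover. A value of 1.20 needs about 12–15 points (for example from 32–35% to 20%). Uptake of 60/30% pre and 65/60% post gives 1.13–1.22 over the same ranges, but implies pre-CP uptake of only 0.15 × 0.60 + 0.85 × 0.30 = 34.5% to 0.25 × 0.60 + 0.75 × 0.30 = 37.5%, below the planned 50%.

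**The case against.** The strongest reply is that a change of case mix is nowhere stated. The portal runs in both phases with the same ratings, item 12a does not confine the handout to the post-CP phase, the email reminders in item 17b are not phase-limited, and item 11a calls its components provisional. All of that stands. A reader might infer from items 11a and 11c that portal promotion switches on with the CP and that case mix therefore does change. The documents do not support that. They support only that the invitation may differ, because item 11c makes the handout part of the implementation strategy and no equal pre-CP invitation is stated. Both readings leave a problem: if the handout is given before the CP, controls receive a listed intervention component; if it is not, the invitation differs by phase.

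A reader might also infer that the plan offers nothing beyond a descriptive table. It does: item 19a adds Cox adjustment, and naming covariates is commonly left to an SAP. But anonymous users cannot be linked to medical records, so severity from that source is unavailable for them whatever the SAP names.

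Finally, the size depends on assumed uptake. When slow-case uptake rises as well, the bias shrinks to 1.04 or 1.01. That also stands.

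**Conclusion.** The concern holds as a risk built into the design. The only source of the primary outcome is voluntary, prompts to use it are listed as intervention components, and the pre-CP invitation is not stated. The route into the analysed sample may therefore change at crossover and bias the hazard ratio in either direction.

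Under the assumptions tabulated, the null hazard ratio lies between about 0.91 and 1.13. It is 1.00 if uptake does not depend on recovery speed, and also if the ratio of slow to fast uptake is the same in both phases. The uptake rates by recovery speed and the 12-week slow median are assumptions; item 6a supplies only the 15–25% share. A reader might conclude that selection alone would produce the design value of 1.20. That needs a fall of 12–15 points in the slow share, and nothing in the protocol indicates a shift of that size. The documents do not establish the direction either. The point should be addressed because later analysis can only partly restore comparability lost at entry.

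**What to change.** 1. Reconcile items 11a, 11c (Table 2) and 12a: state which materials are given in which phase.
2. Separate the invitation from the CP. Use a portal-only flyer and reminder without the educational content, and give it identically in both phases at all sites from the start of data collection. The education pages stay in the CP.
3. Report portal uptake per diagnosed concussion by phase, and by site where users can be assigned to one. Compare portal users with all diagnosed children in the AHS data on the characteristics available. Read this with care, because item 12b predicts that the share of visits diagnosed as concussion will itself rise.
4. Weighting portal users to the AHS totals by age and sex is at most an optional sensitivity analysis, for users who can be placed in cells. Item 17a says only that age is required at portal access. Such weighting does not correct selection on recovery speed within cells.

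**Cost.** Flyers for the pre-CP phase, revised protocol wording and tables from data already planned. There is also a loss of scope: flyer promotion no longer counts as part of the CP effect, and the website-hits adherence outcome (Table 3) would then reflect the CP website content and not its promotion.

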- 9 The four sites, each of which will be treated as a cluster in the analysis, are Alberta Children's Hospital and South Health Campus in Calgary (treated as a single site because they are staffed by the same group of pediatric physicians), and Stollery Children's Hospital, North East Community Health Center, and Grey Nun's Hospital in Edmonton (each of these Edmonton sites is staffed by different physician groups and will therefore be treated separately). The sites were selected because they represent high-volume centres that account for a significant proportion of children diagnosed with concussion in acute care settings in Alberta. Collectively, they accounted for 2,098 concussion diagnoses over 12 months in 2015-2016, as well as another 1,517 cases with the diagnosis of head injury, unspecified, which is often used in place of the more specific diagnostic code (see Table 1 on next page). Our project team includes the emergency medicine physicians who are the academic and clinical leaders for emergency medicine in both Calgary ([name]) and Edmonton ([name]).

All four clinical sites have provided enthusiastic letters of support for the proposed project, and will allocate staff time and provide space for project activities as in-kind contributions. More specifically, the operational leads at the sites have agreed to encourage the participation of their physicians and nurses in the project and to provide space needed for project site visits, key informant interviews, and staff training. The participation of the PI, Co-PIs, and all Co-Investigators is strongly supported by their respective academic institutions.

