#### *Clinical Sites: Edmonton*

The only pediatric emergency facility in central and northern Alberta is at the Stollery Children's Hospital. With its catchment area including the Northwest Territories, Eastern British Columbia, and Western Saskatchewan, the Emergency Department (ED) at Stollery Children's sees approximately 50,000 patients each year. Of those patients, approximately 10% are admitted to hospital. In addition to the Stollery Children's Hospital, children are seen for acute care at several other sites in Edmonton. These include the North East Community Health Center and the Grey Nuns Hospital. Combined, these two sites evaluate approximately 18,000 patients in the Edmonton zone. All three sites have been active in research and have participated in the Alberta Childhood Asthma Pathway implementation, so that they are familiar with CP implementation studies.

|                                 |            |  |
|---------------------------------|------------|--|
| 
Study setting
Cont'd
 | 
9
   | 
Clinical Sites: Calgary
 
The ED at Alberta Children’s Hospital (ACH) provides care for over 77,000 patient visits per year. The department serves as the pediatric tertiary medical and trauma referral center for Southern Alberta, Eastern British Columbia, and Western Saskatchewan, and is the primary pediatric ED for the local area. The ED at ACH is actively involved in concussion clinical care and research. It was a central recruitment site for the local 4C study ([name], PI) and the national 5P concussion ([name], PI) and PLAYGAME ([name], PI) studies, and is currently recruiting for the national A-CAP ([name], PI) concussion study. The South Health Campus ED opened in January 2013 and serves as a satellite pediatric ED care setting to ACH. The same group of pediatric emergency medicine physicians staff the South Health Campus ED 12 hours per day (noon to midnight), to better serve the children and families of south Calgary and the rural communities to the south. Annually, 15,000 children are cared for in the South Health Campus ED.
  |

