Secondary outcomes also will include measures of physician adherence, the number of unique website hits per IP address, the proportion of patient- and parent-reported adherence to physician discharge recommendations, the proportion of diagnosed concussions per visit (predicted to increase as physicians identify and code the injuries correctly), and the proportion of CT scans ordered per diagnosed concussion (predicted to decrease because the CP will include prediction rules for CT scanning in concussion).

12c *Table 3: Process and clinical outcomes*

| Outcome measure      | Description         | Details  |
|-----------------------------|----------------------------|---|
| Primary clinical outcome    | Time to symptom resolution | Weekly ratings by patients and parents of whether patient has returned to pre-injury status   |
| Secondary clinical outcomes | Postconcussive symptoms    | Weekly ratings on Health and Behaviour Inventory  |
|                             | Quality of life            | Weekly ratings on PedsQL  |
|                             | Satisfaction with care     | Post-visit rating of overall satisfaction with acute care   |
| Primary process outcome     | Physician adherence        | Proportion of completed discharge forms per diagnosed concussion    |
| Secondary process outcomes  | Patient/parent adherence   | Proportion of patient and parent reports of adherence to physician discharge recommendations involving rest, return to school, and return to play |
|                             | Patient/parent adherence   | Number of unique website hits per IP address  |
|                             | Physician adherence        | Proportion of diagnosed concussions per visit   |
|                             | Physician adherence        | Proportion of CT scans ordered per diagnosed concussion   |

Qualitative interviews and site surveys resulted in the discharge form being replaced by the 5P risk score sticker. To assess adherence, the study team recorded the number of 5P assessments completed by each site over the course of data collection.

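### Concussions per ED visit is read as physician identification and coding, but with no calendar-time term it also picks up changes in visit volume and injury incidence

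*Protocol*

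**What the plan says.** Table 3 (item 12c) lists "proportion of diagnosed concussions per visit" among the secondary process outcomes and labels it physician adherence. Item 12b gives the expected direction and its meaning: the figure is "predicted to increase as physicians identify and code the injuries correctly". Neither place says which visits are counted.

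Item 9 (Study setting) describes the coding problem. For the participating sites it says: "Collectively, they accounted for 2,098 concussion diagnoses over 12 months in 2015-2016", and adds "another 1,517 cases with the diagnosis of head injury, unspecified, which is often used in place of the more specific diagnostic code". Item 10 defines concussion by ICD code S06.0, brings S09.9 (head injury, unspecified) into a sensitivity analysis, and leaves open that the study may recode some S09.9 cases to S06.0.

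Item 19a says that outcomes other than the primary are analysed with mixed models containing a random effect for cluster and a fixed effect for pathway status before or after implementation. It names no calendar-time term for the main analysis; time since implementation enters only in exploratory analyses. Item 14 plans to summarise total patient volume and concussion counts by exposure status, as description.

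**The concern.** The outcome is meant to show whether physicians recognise concussion and give it the right code. A rate per ED visit responds to that, but also to two other things: how many children attend for unrelated reasons, and how many head injuries occur. Concussion is a small fraction of attendances, so nearly all of the denominator carries no information about concussion coding.

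In a stepped wedge trial this matters more than usual, because every site moves from control to pathway and none moves back. If attendance or injury rates drift over the calendar, a model with only a site effect and a pre/post effect attributes part of that drift to the pathway. The result could be a reported gain in physician adherence that is a volume change, or a real gain that a busier later period hides. The primary outcome and the power calculation are not affected.

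**Working it through.** The protocol states no expected rate or power for this outcome, so there is no figure to reproduce. The check is ratio arithmetic on its own counts.

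**Inputs (item 9).**
- Concussion diagnoses in 12 months: 2,098.
- Head injury, unspecified, in 12 months: 1,517.
- Alberta Children's Hospital: "provides care for over 77,000 patient visits per year".
- South Health Campus: "Annually, 15,000 children are cared for in the South Health Campus ED".
- Stollery: "sees approximately 50,000 patients each year".
- The other two Edmonton sites: about 18,000 patients combined, period not stated, taken here as annual.

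**Baseline.** Volume: 77,000 + 15,000 + 50,000 + 18,000 = about 160,000. Per-visit rate: 2,098 / 160,000 = 1.31%. S06.0 share of the two codes: 2,098 / (2,098 + 1,517) = 2,098 / 3,615 = 58.0%.

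**Effect of a coding change.** If a fraction f of S09.9 cases is coded S06.0 instead, the numerator becomes 2,098 + 1,517f. With coding unchanged, the fall in visits that gives the same per-visit rate is 1 − 2,098 / (2,098 + 1,517f).

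| f | Numerator | Per-visit rate | S06.0 share | Fall in visits giving the same rate |
|---|---|---|---|---|
| 0 | 2,098 | 1.31% | 58.0% | none |
| 10% | 2,249.7 | 1.41% | 62.2% | 6.7% |
| 20% | 2,401.4 | 1.50% | 66.4% | 12.6% |

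The last column does not contain the visit total, so the uncertainty about the 160,000 affects the 1.3% but not the break-even falls. If only visits outside the two codes change (160,000 − 3,615 = 156,385), the falls are 10,789 / 156,385 = 6.9% and 20,215 / 156,385 = 12.9%. Hence about 7% and 13%.

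**Effect of volume or incidence alone, coding unchanged (assumed ranges).** A 10% or 20% fall in unrelated visits gives 1.45% or 1.63%; a 10% or 20% rise gives 1.19% or 1.10%. A 10% to 30% rise in head injuries with the same code mix gives 1.44% to 1.69%. In all of these the S06.0 share stays at 58.0%, given that the mix is held constant.

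**Tie between pathway status and calendar.** Take crossovers at months 2, 4, 6 and 8 of a 10-month trial (item 13a), with equal weight per site-month. A site crossing at month x has mean control time x/2 and mean pathway time (10 + x)/2, a gap of 5 months at every site. Over all sites, the control mean is (2 + 8 + 18 + 32) / 20 = 3.0 months and the pathway mean is (48 + 42 + 32 + 18) / 20 = 7.0 months.

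**The case against.** Several points against this are fair.

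- **The denominator is not defined.** The protocol says only per visit. An age band or a restriction to injury visits may be set in an SAP that is not at hand, and the 1.3% would then change. This stands, and is why the point rests on the plain reading. The protocol does fix how a rise is to be read and which terms the model contains.
- **No seasonal data.** The documents give no monthly volumes, overall or by site. The relevant swing is also a net pre/post difference, not peak to trough, and both conditions run side by side in 6 of the 10 months. The break-even falls show what would suffice, not what will occur.
- **Duration is inconsistent.** Item 13a says about 10 months, the design overview 11, and the power calculation in item 14 assumes 18 months of recruitment. One cannot rely on the trial being shorter than a year. Pathway time follows control time at each site under any of these.
- **The S06.0 share is also imperfect.** It depends on the true mix of injuries within the two codes and misses concussions that were not recognised or were coded elsewhere. Item 12b refers to identification as well as coding.
- **Volume will be visible.** The descriptive summary in item 14 would reveal a large shift, but does not adjust for it.

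A reader might infer that the per-visit rate cannot reflect coding at all, that season outweighs any coding gain, or that the rate should be dropped. The documents do not support this. Raising the S06.0 share to 70% gives 0.70 × 3,615 = 2,531 cases, or 1.58% of visits. An assumed 20% fall in all visits without a coding change gives 2,098 / 128,000 = 1.64%, a narrow margin. A 20% rise together with that coding gain gives 2,531 / 192,000 = 1.32%, which cancels the gain but does not reverse it.

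**Conclusion.** The concern holds in limited form. As planned, the per-visit rate mixes physician coding with visit volume and head-injury incidence, and the model in item 19a does not separate pathway status from calendar time. A net fall in visits of about 7% would be indistinguishable from coding 10% of S09.9 cases as S06.0, and about 13% from 20%. This assumes that visit means any ED visit, that the 2015-2016 counts describe the trial population (their age range is not given), and that the numerator is otherwise stable. Whether swings of that size will occur is unknown. This is a secondary process outcome and the change is small, so it should be made; it does not threaten the main conclusion.

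**What to change.** In item 12b and Table 3, add S06.0/(S06.0+S09.9) among children aged 5 to 18 as the measure of physician coding. Use the code originally assigned in the ED, before any recoding under item 10; otherwise the outcome would partly measure the analysts' coding. Analyse it with the logistic mixed model already planned in item 19a plus a fixed calendar-period term.

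Keep concussions per visit beside it. State which visits are counted, apply the same period term, and do not interpret it alone as coding adherence.

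**Cost.** A few lines of text. Item 10 already plans to use S09.9 cases, but item 18 describes extraction for children diagnosed with concussion, so it should state that S09.9 records are obtained for the whole trial with the original code retained. The share misses concussions given other codes and moves with the injury mix, which is why the per-visit rate stays. A period term removes only shifts common to all sites; with four clusters, site-specific shifts would remain, and a display of both measures by site and month would help to show them.
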